#### **Prenatal Session 2 (34-39 weeks)**

At 34-39 weeks gestation, participants have another session (in-person if pre-COVID or virtual if during COVID), and complete mood assessments, a cognitive assessment, and answer more questions about feelings and sleep. This session takes about 75 minutes. They are asked to wear the activity monitor again for 7 days and complete a sleep diary (5-10 minutes to complete).

All participants are provided with psychoeducation (and an information sheet) that highlights the warning signs of depression and the risks of depression and contact information for research staff so that they can access help and referrals if they begin to experience depression. All participants (regardless of group assignment) are encouraged to contact the study clinician at any point during the study if they are interested in a referral for treatment.

### **Newborn Session (18-36 hours post-delivery)**

Participants are invited to have their newborn participate in an EEG sleep study that occurs between 18-36 hours after birth in the newborn nursery. We will examine variation in EEG left/right power asymmetry in relation to potential group differences in the effectiveness of the intervention in helping mothers function as a social "buffer" and modulate infant reactivity. The newborn EEG sleep protocol takes place in the newborn nursery while the baby is sleeping. This is a non-clinical EEG recording. A cap with EEG sensors is placed on the newborn's head by a trained member of the research team. The research team then waits for the baby to enter a state of quiet sleep. This allows the research team time to measure brain activity while the baby sleeps. The participant is reassured by the research team that although the sensors may leave a slight red mark for a brief time after they are removed, this procedure is completely painless and does not harm the newborn.

The EEG session takes approximately 30 minutes. This session is video recorded to allow the researchers to collect information about newborn behavior during the session. In total, including setup of materials and video-recording, the session is approximately 1.5 hours in duration.

The participant is allowed extra time to pick up, feed, comfort, or change the newborn to accommodate fussiness or discomfort at any time during the EEG. If the participant is uncomfortable with the EEG, they were free to stop the session.

If the participant gives birth prior to 37 weeks, they do not complete this EEG session with their newborn. The participant is still be able to proceed with the rest of the study. Participants did not complete this session during the COVID pandemic.

## **6-Week Postpartum Session**

At 6 weeks postpartum, participants are asked to participate in another session (in-person if pre-COVID or virtual if during COVID), to complete mood assessments. This session is about an hour. During this session, participants are videotaped as they engage in a standard routine of infant care. This takes about 5 minutes to complete.

If the session is completed in-person (not virtually), participants are invited to complete the infant EEG. We will examine variation in EEG left/right power asymmetry in relation to potential group differences in the effectiveness of the intervention in helping mothers function as a social "buffer" and modulate infant reactivity. The 6-week postpartum EEG sleep protocol takes place while the baby is sleeping. This is a non-clinical EEG recording. A cap with EEG sensors is placed on the newborn's head by a trained member of the research team. The research team then waits for the baby to enter a state of quiet sleep. This allows the research team time to measure brain activity while the baby sleeps. The participant is reassured by the research team that although the sensors might leave a red mark briefly after they are removed, this procedure is completely painless and does not harm the newborn.

The EEG session takes approximately 30 minutes. This session is video recorded to allow the researchers to collect information about infant behavior during the session. In total, including setup of materials and video-recording, the 6-week EEG session is approximately 1.5 hours in duration.

The participant is allowed extra time to pick up, feed, comfort, or change the infant to accommodate fussiness or discomfort at any time during the EEG. If the participant is uncomfortable with the EEG, they are free to stop the session.

Participants wear an activity monitor again for 7 full days. While wearing the monitors, participants complete a sleep diary noting sleep times and durations, which takes about 5-10 minutes. Participants in the treatment group are asked to complete a diary entry that asks them the frequency and duration of their utilization of the skills learned from PREPP (i.e., carrying/holding baby, accentuation of day/night cues, focal feeding, use of swaddling,

mindfulness techniques). These questions take about 10 minutes to complete. Infant sleep is assessed using a Smart Sleep Sensor worn by the infant. The Sensor detects day and night sleep activity by recording activity patterns during the time intervals in which it is worn. Infants wear the Sensor for four days (24- hour periods).

### **12-Week Phone Session**

At 12 weeks postpartum, participants complete mood assessments over the phone. This takes about an hour to complete.

### **16-Week Postpartum Session**

At 16 weeks postpartum, participants are asked to participate in a final session (in-person if pre-COVID or virtual if during COVID) to complete mood assessments and other questions related to feelings, life events, and sleep. Participants are asked again to complete a questionnaire about the effect of COVID-19 on their lives (if during COVID pandemic).

All together, these questionnaires take an hour to complete. Participants are asked to sit on the floor and play with their baby using a set of toys they usually use at home. They are asked to engage in free play for 10 minutes, and their play interaction is videorecorded and later coded using the Emotional Availability (EA) Scales. Mothers and infants are also asked to participate in a modified 'double' Still Face Protocol (SFP), an A-B-A-B-A design with alternating free-play (A) and still-face (B) periods. The entire SFP session is videotaped for later behavioral coding. The session begins with five minutes of face-to-face free play, followed by a two-minute still-face episode. Two additional free-play periods and a second still-face episode, each lasting two minutes, follows. A study coordinator signals transitions by saying "Switch". If the infant cries for more than 30 seconds or intensely for over five seconds, the session is stopped so the mother can comfort the infant. The full procedure lasts about 20 minutes. Frequency of infant positive affect, signs of avoidance (infant head turn and back arch), and duration of infant distress/crying and neutral/positive vocalizations will be coded. Mothers will be coded for duration of vocalizations to the infant, touching the infant, and positive/negative affect.

During this session, participants are also videotaped as they engage in a standard routine of infant care. This takes about 5 minutes to complete.

For a final time, participants wear the activity monitor again for 7 days. Participants complete a sleep diary noting sleep times and durations, which takes them 5-10 minutes to complete.

Participants in the treatment group complete a diary entry asking them about the frequency and duration of their utilization of PREPP skills. Infant sleep is assessed using a Smart Sleep Sensor worn by the infant. The Sensor detects day and night sleep activity by recording activity patterns during the time intervals in which it is worn. Infants wear the Sensor for four days (24- hour periods).

### Table

Session	Task	Time Commitment
Prenatal: 28-32 weeks	Questions about mood and COVID-19, cognitive assessment	90 minutes
Prenatal: 34-39 weeks	Questions about mood, cognitive assessment	75 minutes
Newborn: 18-36 hours	Infant EEG	1.5 hours
Postpartum: 6 weeks	Questions about mood, cognitive assessment, infant care routine, Infant EEG	2.5 hours
Postpartum: 12 weeks (on the phone)	Questions about mood and cognitive assessment	60 minutes
Postpartum: 16 weeks	Questions about mood and COVID-19, cognitive assessment, Infant care routine, Mom/Baby play	2.5 hours

### Baby Day Diaries

At 6 and 16 weeks postpartum, mothers are asked to complete four consecutive days of 24-hour diaries describing infant and parental behavior (the Baby Day Diary). The diaries allow for notation of infant cry, fuss, and awake-content, feeding and sleeping activity. Caregiving behavior is also noted, including; changing, bathing, dressing, holding/carrying and playing/talking behaviors as well as their own sleep periods. Baby diaries take about 30 minutes to complete.

### List of Instruments and Standardized Protocols:

Data Collection Instrument	Screening (20-29 weeks)	Prenatal 1 (28-32 weeks)	Prenatal 2 (34-39 weeks)	Newborn	6 week	12 week	16 week
Demographics		X	X		X	X	X
Newborn Delivery Data				X			
Pregnancy Medical History	X						

Predictive Index of Postnatal Depression (PIPD)	X						
Mini International Neuropsychiatric Interview (MINI)	X						
Columbia Suicide Severity Rating Scale (C-SSRS)	X	X	X		X	X	X
Edinburgh Postnatal Depression Scale (EPDS)	X	X	X		X	X	X
Hamilton Anxiety Scale (HRSA)	X	X	X		X	X	X
Hamilton Depression Scale (HRSD)	X	X	X		X	X	X
Personal Health Questionnaire-9 (PHQ-9)		X	X		X	X	X
Pittsburgh Sleep Quality Index (PSQI)		X	X		X	X	X
Pregnancy Physical Activity Questionnaire (PPAQ)		X	X				
Family History Screen (FHS)				X			
Adverse Childhood Experiences Questionnaire (ACE)		X					
Benevolent Childhood Experiences scale (BCEs)		X					
The Hunger Vital Sign (HVS)		X	X		X		X
Experiences in Close Relationships (ECR)		X					
Childhood Trauma Questionnaire (CTQ)		X					
Multidimensional Scale of Perceived Social Support Questionnaire (MSPSS)		X			X		
Maternal Antenatal Attachment Scale (MAAS)			X				
Abbreviated Brief Infant Sleep Questionnaire (BISQ)					X		X
Childcare Arrangement Scale (CAS)					X		X
Infant Intentionality Questionnaire (IIQ)					X		X
Infant Nutrition Questionnaire (INQ)					X		X
Karitane Parenting Confidence Scale (KPCS)					X		X
Short Acculturation Scale for Hispanics (SASH)			X				
Experiences of Discrimination (EOD)			X				

Adult Attachment Questionnaire (AAQ)		X	X				
Maternal Postnatal Attachment Scale (MPAS)					X		X
Being a Mother (BaM-13)							X
Parental Bonding Instrument for Mothers (PBI-M)		X	X				
Parental Bonding Instrument for Fathers (PBI-F)		X	X				
Rejection Sensitivity Questionnaire (RSQ)		X					
Difficulties in Emotion Regulation Scale (DERS)		X	X		X		
Interpersonal Support Evaluation List (ISEL)		X					
COVID-19 Questionnaire		X					X
Utilization of PREPP Skills		X	X		X		X
Infant EEG				X	X		
Adult Activity Monitor		X	X		X		X
Sleep Log		X	X		X		X
Infant Smart Sleep Sensor					X		X
Baby Day Diary					X		X
Infant Care Routine, video					X		X
Modified 'double' Still Face Protocol, video (SFP)							X
Free Play, Video							X

### Treatment Protocols:

#### Experimental Arm: PREPP Intervention

The intervention is carried out at 5 timepoints, Session 1 at 28-32 gestational weeks, Session 2 at 34-39 gestational weeks, Session 3 at 6 weeks postpartum, Check-In Session 1 within 3 days of the birth and at Check 2 Session at 2 weeks postpartum. These sessions are scheduled to coincide with standard medical visits (3rd trimester ultrasounds and 6-Week Well Baby visit), which enable us to test the feasibility of incorporating these sessions into routine medical care. A licensed trained clinician or an unlicensed trained clinician under licensed supervision provide the intervention. The sessions of this preventive psychotherapy are comprised of three

components: (a) mindfulness and self-reflection skills, (b) parenting skills and (c)psycho-education. The intervention protocol encompasses the following 5 specific established behavioral techniques: (1) feeding the infant between 10 pm and midnight, even if s/he must be awakened ('a focal feed'); (2) accentuating differences between day and night cues so that there are higher levels of stimulation during the former than the latter; (3) assuming adequate weight gain is reached by 3 weeks, lengthening the latency to feeding time in the middle of the night by engaging in other attentive activities such as walking with the baby and diapering; the goal is to lengthen the nighttime feeding intervals by extinguishing the association between night time waking and feeding; (4) carrying infants for a minimum of 3 hours a day, throughout the day, independent of responding to crying, carrying during feeding, and whether the baby is awake; and (5) learning to swaddle the baby as a possible soothing intervention. Mindfulness-based tools are provided with the aim to (1) aid them to return to sleep after waking at night, (2) help them to cope better when their babies are distressed or unsoothable. These mindfulness exercises are provided as audio files via an App.

#### **Active Comparator: Enhanced Treatment As Usual (ETAU):**

ETAU comprises Postpartum Depression psychoeducation, mood assessments, and referral for treatment if needed or requested by the participant. Three sessions are delivered by licensed trained clinician or an unlicensed trained clinician under licensed supervision. Participants receive "usual care" along with Postpartum Depression psychoeducation and enhanced support for finding perinatal mental healthcare treatment when appropriate by meeting with a study clinician specifically assigned to provide ETAU in this study at three times that are aligned with PREPP sessions that span from pregnancy to 6 weeks postpartum. At the first contact, participants meet with their assigned ETAU clinician and are given information about PPD, a brief clinical mental health assessment, and a referral for treatment if warranted or requested; the second session is a follow-up mental health clinical assessment with the study clinician and a referral for treatment if warranted or requested; at the third session, participants meet again with their study clinician and receive a mental health assessment, review relevant psychoeducation on PPD and are referred to treatment when appropriate.

#### **Statistical Analysis Plan**

**Overall.** Based on preliminary data, we anticipate minimal attrition ( $\leq 5\%$ ) during the first two assessment sessions (pre-delivery), and up to 33% attrition postpartum across both groups in the worst-case scenario. All participants with data available for a given study phase (pre- or postpartum) will be included in the primary analyses. Before conducting hypothesis tests, we will screen all variables at all time points for out-of-range values, outliers, and data inconsistencies. Means, standard deviations, interquartile range, minima, and maxima for continuous variables and proportions for categorical variables will be reported.

Following CONSORT guidelines, the primary analyses for all aims will follow an intention-to-treat (ITT) approach, including all randomized participants regardless of treatment adherence or dropout. If significant imbalances in baseline covariates (e.g., maternal age, BMI, birth order, infant sex) are observed despite randomization, these variables will be included as covariates in the models. Additional exploratory models will examine relevant biological factors, such as maternal BMI, fetal/infant sex, maternal age, infant gestational age at birth, and birthweight corrected for birth age, as potential covariates.

**Aim 1.** Reduce women's distress during pregnancy. We hypothesize that PREPP will be associated with: (A) Diminished depressive symptoms using interviewer-rated and self-report questionnaires; (B) Improved perception of sleep quality relative to objective changes in sleep duration (per self report and actigraphy).

**Analysis for Aim 1A:** For depressive symptom outcomes (HRSD, PHQ-9, HRSA, PSQI, EPDS), we will fit linear mixed-effects models with fixed effects for Treatment (PREPP vs. ETau), Time (2nd and 3rd assessments), and birth order, along with subject-specific random intercepts. For EPDS, we will adjust for the screening score and test a Treatment  $\times$  Screening Score interaction as a secondary analysis. Additional moderators will also be tested.

**Analysis for Aim 1B:** Two ActiGraph-derived measures, total sleep time (TSTact) and sleep efficiency (SEact), will serve as outcomes in separate mixed-effects models with fixed effects for time and day (within the ActiGraph epoch) and subject-specific random intercepts, assuming an AR(1) correlation structure. We will assess whether adjustment for weekday/weekend is warranted. Subject-specific means of these measures will be used as predictors of their subjective

counterparts (TSTact, SEact) in additional mixed models testing for treatment group differences in the association between objective and subjective sleep measures. Moderation by trauma history and attachment will be explored.

**Aim 2. Determine the maintenance of improved maternal mood and differences in infant behavior.** We hypothesize that PREPP will be associated with: (A) Lower rates of PPD and distress, including poor sleep efficiency, assessed by interviewer-rated and self-report questionnaires as well as sleep actigraphy. (B) Less infant fuss/cry behavior and longer nocturnal sleep bouts based on maternal report and actigraphy.

**Analysis for Aim 2A:** Separate linear mixed-effects models will be used for each maternal mood outcome (PHQ-9, HRSD, EPDS, HRSA, PSQI) and ActiGraph-derived sleep measures. Models will include Treatment, Time (6, 12, and 16 weeks postpartum), and their interaction, with baseline (pregnancy) values as covariates. Subject-specific random intercepts will be included. The primary parameter of interest is the Treatment  $\times$  Time interaction; if non-significant, the main effect of Treatment will be tested. PPD diagnosis will be modeled using mixed-effects logistic regression with analogous fixed effects.

For infant outcomes (6 and 16 weeks), linear mixed-effects models will assess Treatment effects without Time  $\times$  Treatment interaction. Sleep data will be processed as in Aim 1B. Covariates include time-varying factors such as weaning, solid food introduction, maternal return to work, and social support. Moderators (infant sex, trauma history, attachment) will also be assessed.

**Analysis for Aim 2B:** Infant sleep and cry behavior at 6 and 16 weeks will be compared using mixed-effects models with Treatment, Time, and their interaction as fixed effects. Covariates and secondary analyses will be same as those in Aim 2A.

**Aim 3. Identify some of the pathways by which PREPP positively affects the dyad.** We hypothesize that PREPP-associated: (A) Lower depression scores postpartum will be mediated by concurrent and/or temporally earlier maternal reports of less infant fuss/cry behavior and higher parenting competence; (B) Less infant fuss/cry behavior will be mediated by fewer concurrent and/or temporally earlier negative infant attributions and higher concurrent observed maternal sensitivity; (C) More positive perceptions and objective assessments of maternal

postpartum sleep efficiency will be mediated by greater infant left frontal EEG power reflecting sleep spindle activity and associated longer average durations of infant nocturnal sleep per maternal report and actigraphy.

**Analysis for Aim 3:** Structural equation models will be used to test multiple-mediation. The mediation and Lavaan R packages will be used for this modeling as it can accommodate both continuous and ordered categorical (including dichotomous) variables. Indirect effects (i.e. combined mediational pathways) will be tested using the bootstrapping with 10000 resampling. Specifically for Aim 3A, we will test whether the effect of PREPP on maternal depressive symptoms at week 16 is mediated by infant fuss/cry behavior and higher parenting competence assessed at 6 and 16 weeks after delivery. A model without inclusion of week 16 mediators will also be considered (due to the contemporaneity of week 16 with the outcome). For Aim 3B, the primary outcome is infant fuss/cry behavior at week 16 and mediators are the maternal reports of negative infant attribution assessed at 6 and 16 weeks after delivery and maternal sensitivity at week 16 after delivery. Because of the concurrently observed mediators and outcomes, alternative mediational pathways will be evaluated and compared. For Aim 3C, a mediation model with EEG power at week 6 and avg. infant sleep (actigraphy) quality will be assessed as mediators of the treatment effect on maternal sleep at week 16, controlling for EEG power at birth as a covariate.

**Power analysis** We adjusted for multiple comparisons (five primary outcomes across Aims 1 and 2) using Bonferroni correction, resulting in a significance threshold of 0.01. For Aim 1, with  $N = 214$  and an assumed 5% attrition, our mixed-effects model analysis is powered to detect a minimum effect size of  $d = 0.48$  (assuming within-subject correlation  $r = 0.2$ ). Prior research has shown larger effects (e.g.,  $d = 0.85$  for EPDS in mindfulness-based therapy), indicating our design has ample power. For Aim 2, assuming 33% attrition and five primary outcomes, power calculations show that  $N = 107$  per group is sufficient to detect interactions as small as  $d = 0.087$  with 80% power at a Bonferroni-adjusted  $\alpha = 0.01$ . Our preliminary data support this assumption. For Aim 3, based on tabulated recommendations 184 for sample sizes needed to test mediation effects, with  $N=142$  completers (assuming 33% attrition for assessments), we have more than 80% power to detect a significant mediation effect with moderate effect sizes ( $d=0.54$ ,

$r=0.26$  of both paths (i.e. the paths from treatment to the mediator(s) and the mediator(s) to outcomes). Since the full sample ( $N = 214$ ) will be used in mediation models, the actual power will exceed this estimate.

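### Further covariates join the primary models only if an undefined significant imbalance appears, while Aim 1A leaves pre-randomisation HRSD and HRSA scores unused

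*Combined protocol and SAP*

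**What the plan says.** The Overall part of the Statistical Analysis Plan, directly after the intention-to-treat statement for the primary analyses of all aims, sets a conditional rule: "If significant imbalances in baseline covariates (e.g., maternal age, BMI, birth order, infant sex) are observed despite randomization", then "these variables will be included as covariates in the models". The next sentence places other variables outside the primary models: "Additional exploratory models will examine relevant biological factors". No test, significance level or complete list of candidates is given.

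The aim-specific paragraphs fix some covariates in advance:

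- **Aim 1A:** every model has fixed effects for treatment, time "and birth order, along with subject-specific random intercepts". One outcome also has a baseline term: "For EPDS, we will adjust for the screening score and test a Treatment" by screening-score interaction, the latter as a secondary analysis. No baseline term is stated for HRSD, HRSA, PHQ-9 or PSQI.
- **Aim 2A, maternal outcomes:** the models are fitted "with baseline (pregnancy) values as covariates".
- **Aim 2, infant outcomes:** "Covariates include time-varying factors such as weaning, solid food introduction, maternal return to work, and social support".

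The Baseline Assessment at 20-29 weeks includes both Hamilton scales. In the List of Instruments, the row beginning "Hamilton Depression Scale (HRSD" is marked at screening, as are HRSA and EPDS. PHQ-9 and PSQI first appear at Prenatal 1. Randomisation takes place at Prenatal Session 1, 28-32 weeks.

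**The concern.** Under proper randomisation, any difference between arms in a baseline variable is chance. A significance test of that difference tests a null hypothesis known to be true, and its result does not show whether the variable predicts mood. A covariate that matters is left out when it happens to be balanced; one that does not matter is added when it happens not to be.

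Because the trigger is undefined and the list is open, the primary models cannot be written down in full before the data are seen. Two analysts following this text could fit different models to the same data.

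Birth order is a specific conflict: the Overall rule treats it as conditional on imbalance, while Aim 1A always includes it.

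Precision is a second matter. For HRSD and HRSA in Aim 1A, a score on the same scale exists before randomisation and is not used, although the plan does this for EPDS in Aim 1A and for the maternal outcomes in Aim 2A.

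**Working it through.** **Inputs from the Power analysis paragraph.** N = 214 (107 per group), 5% attrition for Aim 1, alpha 0.01 after Bonferroni for five primary outcomes, d = 0.48, within-subject r = 0.2.

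**Assumptions.** Two-sided test; 80% power for Aim 1 (stated only for Aim 2); SD = 1; imbalance tested at 0.05; correlation rho between a baseline covariate and the outcome at each assessment, which the documents do not give.

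**1. Reproducing d = 0.48.** Per arm, n = 214 × 0.95 / 2 = 101.65. The minimum detectable effect is (2.576 + 0.842) × √(2/101.65) = 0.479. Power at d = 0.48 is 80.1%. The stated figure therefore matches an unadjusted comparison at a single assessment.

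**2. Chance flags.** Independent covariates, each tested at 0.05:

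- four named covariates: 1 − 0.95⁴ = 18.5%;
- three, since birth order is already fixed in Aim 1A: 1 − 0.95³ = 14.3%.

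**3. Single-assessment power at d = 0.48.** Adjustment multiplies the SD by √(1 − rho²). The conditional rule was simulated with one covariate and 102 per arm (40,000 replicates for power, 100,000 under the null).

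| rho | Always adjusted, formula | Always adjusted, simulated | Conditional rule, simulated | Type I error of the rule (nominal 1%) |
|---|---|---|---|---|
| 0.2 | 82.0% | 81.3% | 79.8% | 0.95% |
| 0.3 | 84.4% | 83.6% | 79.8% | 0.91% |
| 0.5 | 91.6% | 91.2% | 80.9% | 0.78% |

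The rule adjusts for a given covariate in only about 5% of trials, so its power stays close to the unadjusted value.

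**4. Planned two-assessment model.** The mean of two assessments with r = 0.2 has variance (1 + 0.2)/2 = 0.6. Adjusting for a covariate with correlation rho to each assessment leaves 0.6 − rho². Power is Φ(0.48 / √(2v/101.65) − 2.576), where v is that variance.

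| rho | v | Power |
|---|---|---|
| none | 0.600 | 96.7% |
| 0.2 | 0.560 | 97.7% |
| 0.3 | 0.510 | 98.7% |
| 0.45 | 0.398 | 99.8% |

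With r = 0.2 and a residual correlation that is not negative, as a random-intercept model implies, rho cannot exceed √0.2 ≈ 0.45. The 0.5 row in step 3 therefore lies outside the plan's own assumption.

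**The case against.** The strongest reply is that the plan already fixes much of what matters. Birth order is in every Aim 1A model, the EPDS model has its screening score, and the Aim 2A maternal models have baseline values. A reader might infer that covariates enter only through the imbalance rule, or that the plan gives up baseline adjustment generally. The documents do not support either reading. The precision point is chiefly about HRSD and HRSA in Aim 1A. It does not apply to Aim 2A maternal outcomes or, as written, to EPDS in Aim 1A.

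A reader might also infer a large loss of power, about 10 points at rho = 0.5. That comes from a single-assessment comparison with an assumed correlation. Nothing in the documents suggests that maternal age, BMI, birth order or infant sex correlate that strongly with mood, and the planned analysis uses two assessments. This objection stands, and the size is reduced accordingly.

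Nor does the rule produce false positives: in simulation it is slightly conservative.

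Birth order could be read as fixed in Aim 1A and conditional elsewhere. That is possible, but the text does not say so, and the Overall rule makes no exception. Similarly, an open list does not exclude HRSD or HRSA, but under the rule they would enter only after a chance imbalance.

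None of this supplies a test, a threshold or a closed list.

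**Conclusion.** The point holds in limited form. The Overall rule leaves the primary models partly dependent on the data through a trigger that carries no prognostic information, and it is inconsistent with Aim 1A on birth order. Aim 1A does not use the screening HRSD and HRSA scores.

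Chance alone would bring in at least one named covariate in 18.5% of trials, or 14.3% for the three not fixed in Aim 1A. Both figures assume independent tests at 0.05, a level the plan does not state.

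On the single-assessment formula behind d = 0.48, always adjusting gives about 81-82% power at rho 0.2, 84% at 0.3 and 91% at 0.5, against about 80-81% under the rule. In the planned two-assessment model at r = 0.2 the gain is about 1 to 3 points on 96.7%. All of these rest on assumed baseline-outcome correlations. The main reason to change the rule is therefore that the model should be fixed in advance; the gain in power is secondary.

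**What to change.** - Delete the significance-triggered rule. Present baseline balance descriptively, without p-values.
- Fix the Aim 1A covariates in advance: birth order in all models; the screening score on the same scale for HRSD, HRSA and EPDS; screening EPDS for PHQ-9 and PSQI, which have no screening value of their own.
- Keep the same-scale baseline adjustment already planned for Aim 2A. A single covariate set imposed on all aims would replace the PHQ-9 and PSQI baselines there with a different scale.
- State whether birth order is also in the Aim 2 models.

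The cost is SAP wording and one or two degrees of freedom per model. No new data are needed.

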#### **Prenatal Session 1 (28-32 weeks gestation)**

At this time point, if the individual agrees to participate in this session and gives consent, the individual is randomly assigned to one of two groups: Intervention vs. Enhanced Treatment As Usual (ETAU). When the participants are 28-32 weeks pregnant, they participate in an in-person session (pre-COVID) or in a virtual session (during COVID), either by phone or video call, and are asked to complete mood assessments, a cognitive assessments and answer questionnaires about feelings, life events, and sleep. Participants are asked a questionnaire about the effect of COVID-19 on their lives. In total, these questionnaires take about 90 minutes. All questionnaire results are entered in Redcap, an online secure database. All information entered in REDCap is de-identified using a screen ID. At home, we ask participants to wear an activity monitor for 7 full 24-hour days. We ask participants to complete a sleep diary noting sleep times and durations for the seven consecutive days they are wearing the activity monitor.

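### Aim 1A: the stated detectable effect (d = 0.48, r = 0.2) does not match the written two-visit model, HRSD and HRSA are left unadjusted for screening values, and the order of the 28-32-week scales and PREPP Session 1 is not given

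*Combined protocol and SAP*

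**What the plan says.** Aim 1 concerns women's "distress during pregnancy. We hypothesize that PREPP will be associated with" lower depressive symptoms and better perceived sleep quality. For HRSD, PHQ-9, HRSA, PSQI and EPDS, the SAP (Analysis for Aim 1A) states: "we will fit linear mixed-effects models with fixed effects for Treatment (PREPP vs. ETau), Time (2nd and 3rd assessments), and birth order", plus subject-specific random intercepts. It lists no Treatment × Time term. Only EPDS is adjusted for its screening score.

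On timing, the section on Prenatal Session 1 (28-32 weeks) says that "the individual is randomly assigned to one of two groups: Intervention vs. Enhanced Treatment As Usual (ETAU"), and the mood scales are completed in that session. Under Treatment Protocols, "The intervention is carried out at 5 timepoints, Session 1 at 28-32 gestational weeks, Session 2 at 34-39 gestational weeks". ETAU contacts take place "at three times that are aligned with PREPP sessions that span from pregnancy to 6 weeks postpartum".

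On power, the SAP sets alpha at 0.01 for five primary outcomes. With N = 214 and 5% attrition, it says that "our mixed-effects model analysis is powered to detect a minimum effect size of" d = 0.48, assuming a within-subject correlation of 0.2. No power level is attached to that sentence. The phrase "with 80% power at a Bonferroni-adjusted" alpha belongs to Aim 2, and Aim 3 has its own 80% statement.

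**The concern.** A mixed model with Treatment and Time main effects, a random intercept and complete data on two visits estimates the between-arm difference in subject means, which is the average of the two visit-specific differences. Averaging two visits correlated at 0.2 should give a clearly smaller detectable effect than one visit does. A quoted figure that shows no such gain suggests that the power statement and the analysis describe different tests.

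The list of instruments shows EPDS, HRSD and HRSA all collected at screening, and the Baseline Assessment section confirms the two Hamilton scales at 20-29 weeks. Adjusting one of the three and not the others gives up precision for no stated reason.

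The first of the two averaged visits is most likely the randomisation visit, which shares its window with PREPP Session 1. Whether the average is a treatment effect over two treated visits or half of one treated difference depends on whether the scales come before or after that session. At stake are attenuation and power.

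**Working it through.** **Inputs.** From the power analysis: N = 214, 107 per group (so 1:1), 5% attrition for Aim 1, alpha 0.01, r = 0.2. Assumed because not stated for Aim 1: 80% power and a two-sided test. Then n = 214 × 0.95 / 2 = 101.65 per arm, and z = 2.576 + 0.842 = 3.418.

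**Reproducing 0.48.** One visit, two samples: SE = √(2/101.65) = 0.1403, so d = 3.418 × 0.1403 = 0.479 (0.483 with the t distribution). This matches the plan, and r does not enter.

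**The written model.** Mean of two visits: SE² = (2/n)(1 + r)/2.
- r = 0.2: SE = √(2 × 0.60/101.65) = 0.1087; d = 0.371 (t-based 0.374).
- r = 0.5 (my range, not in the documents): SE = 0.1215; d = 0.415.

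**Can another reading rescue 0.48?** At r = 0.2 the two-visit model gives 0.419 at 90% power and 0.459 at 95%. One-sided alpha 0.01 gives 0.344. Scaling by the residual SD gives 0.371/√0.8 = 0.415. Scaling by the SD of the two-visit mean gives 0.371/√0.6 = 0.479, but r then cancels.

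**Screening adjustment.** If the screening value also correlates at r with each visit, the variance factor falls from (1 + r)/2 to (1 + r)/2 − r².
- r = 0.2: 0.60 to 0.56, a cut of 0.04/0.60 = 7%; d = 0.359.
- r = 0.5: 0.75 to 0.50, a cut of 33%; d = 0.339.

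PHQ-9 and PSQI have no screening measurement, so they stay at 0.371 (0.415 at r = 0.5). EPDS already has the adjustment in the written model.

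**Which visits?** The instrument list runs Screening, Prenatal 1, Prenatal 2, and Aim 1 is confined to pregnancy, so the second and third assessments are most likely Prenatal 1 (28-32 weeks) and Prenatal 2 (34-39 weeks). This is an inference: the attrition sentence in the same SAP counts the pre-delivery sessions as first and second.

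**Which order at Prenatal 1?** No section says. Two weak hints lean towards scales after the session: the Prenatal 1 text mentions assignment before the questionnaires, and the instrument list schedules "Utilization of PREPP Skills" at Prenatal 1. Neither fixes when the mood scales are given.

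**If the scales precede Session 1.** The averaged effect is half the 34-39-week effect. Power = Φ(effect/SE − 2.576), r = 0.2:

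| 34-39-week effect | Average, no early effect | 34-39-week contrast alone |
|---|---|---|
| 0.48 | 0.24/0.1087: 36% | 0.48/0.1403: 80% |
| 0.70 | 0.35/0.1087: 74% | 99% |
| 0.85 | 0.425/0.1087: 91% | nearly 100% |

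**If they follow it.** With a 34-39-week effect of 0.48 and an early effect of 0, 25, 50, 75 or 100% of it, the averaged test has 36, 57, 77, 90 or 97% power, against 80% for the single contrast. It becomes the stronger test once the early effect exceeds 2√0.6 − 1 = 55% of the later one.

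**The case against.** A reader might infer that Aim 1A wrongly mixes a pre-treatment visit into its treatment effect, so that the analysis is badly underpowered. The documents do not support that. They leave the order open, and what hints they give point the other way. If both visits follow Session 1, a main-effect model is an ordinary choice. Even in the adverse case the loss depends on the true effect: at 0.48 and r = 0.2 the ratio is 36/80 = 0.45, while at the 0.85 that the plan cites for EPDS in mindfulness-based therapy 91% power remains. That figure comes from another therapy and may be optimistic, but it belongs in the picture.

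A reader might also infer that 0.48 is an error that makes the trial too small. No section calls it a single-visit figure; that follows only from the arithmetic, under assumed power and sidedness. For an effect constant over both visits it errs on the safe side. Leaving HRSD and HRSA unadjusted costs precision and introduces no bias.

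All of this stands, and it narrows the point. It does not remove the mismatch between the quoted d and the written model, or the uneven adjustment.

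**Conclusion.** Two parts are firm. The stated d = 0.48 with r = 0.2 does not describe the written two-visit test, which at 80% power, two-sided alpha 0.01 and 101.65 per arm detects about 0.37 in single-visit SDs (0.42 at r = 0.5). And HRSD and HRSA are measured before randomisation but not adjusted for, which forgoes a variance reduction of about 7% at r = 0.2 and 33% at r = 0.5, if the screening correlation equals r.

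The third part is conditional. If the 28-32-week scales precede PREPP Session 1, the Aim 1A coefficient is half the 34-39-week effect and loses power as tabulated. If they follow it, the average is legitimate and may be the better test. Nothing here implies false-positive inflation. The point merits correction in the SAP but does not threaten the validity of the trial.

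**What to change.** 1. Restate the detectable d for the test actually used, with its power, sidedness, SD scale and r, by outcome. For the two-visit average of a constant effect: about 0.37 for PHQ-9 and PSQI; about 0.36 for EPDS, and for HRSD and HRSA once adjusted, if the screening correlation is also 0.2. At r = 0.5 these become 0.42 and 0.34.
2. Adjust HRSD and HRSA for their screening values, as is already done for EPDS.
3. Name the Aim 1A visits by gestational week. Establish from the study procedures, blind to outcome data, whether the Prenatal 1 scales came before allocation and before Session 1.
   - If before Session 1: test the 34-39-week difference, and use Prenatal 1 as a baseline provided the participant did not yet know her arm.
   - Otherwise: keep the averaged effect as the test, keep Prenatal 1 out of the covariates, and report the 34-39-week difference as a prespecified secondary estimate.

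The cost is SAP wording and a check of procedures; no new data are needed. Items 1 and 2 have no downside. Item 3 must stay conditional: switching to the single contrast when both visits follow treatment would reduce power from 97% to 80% at equal effects of 0.48 and r = 0.2. The document is dated November 2024 and describes some procedures in the past tense, so the choice of test should be fixed and documented before anyone looks at outcomes by arm.
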